9.1 Definition of adverse events

Adverse events (Adverse event, AE) are any signs, symptoms or clinical manifestations that are inconsistent with the treatment purpose, even if there is no correlation with the treatment, is to be recorded and followed up for their regression.

9.2 Record of adverse events

Record all adverse events that occurred after signing the informed consent form. The contents of each adverse event record should include the following points:

- Duration of the adverse event : start time and end time;
- **2**Severity of adverse events:

Mild-no impairment, no need stopping trial Moderate-some impairment, need stopping trial, no need for intervention Severe-evidence of impairment, need stopping trial and need for intervention;

• Relationship between adverse events and intervention: Investigators assessed the correlation between adverse events and the intervention as: positive / likely related

/ possibly related / likely unrelated / unrelated;

4 Management of adverse events: The investigator should follow up the adverse events until the symptoms disappear or stabilize; if the adverse event remains at the end of the study, follow up again within one month after the end of the study.

The intervention used in this study is rTMS, in principle, there is no safety risk in the use of rTMS in children if the safety guidelines developed by the international expert panel are strictly adhered to. However, rTMS may bring temporary minor discomfort such as scalp discomfort, localized pain, dizziness, headache, fatigue, tinnitus, anxiety, etc., mostly relieved within 24 hours. Serious side effects of seizures and neurocardiogenic syncope induced during stimulation have also been reported, but subjects who experienced these two adverse reactions had a history of depression and/or syncope.

The intervention process of this study is conducted in the hospital, and the subjects will be closely followed and supported in case of adverse reactions; if medical treatment is needed, the pediatrician will provide the treatment plan and follow-up visits. In addition, the study will continue to follow up the adverse events within 4 weeks after the 5-day intervention.

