4.4 Exclusion criteria

- A. With metal implants in the body
- B. History of epilepsy or other neurological disease
- C. Require surgical treatment due to structural abnormalities indicated by brain MRI
- D. With genetic or chromosomal abnormalities
- E. With psychiatric/mental disorder (e.g., very early-onset schizophrenia) other

than ASD

- F. Suffer from serious heart disease and/or severe hearing impairment
- G. Intracranial hypertension
- H. Participating in other clinical trials
- I. Participants who received other interventions within 4 weeks prior to enrollment.

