6.0 Follow-up plan

6.1 Follow-up time arrangement

- Total of three follow-up time.
- Follow-up visit 1 (V0): Baseline
- Follow-up visit 2 (V1): immediately after the 5-day intervention
- Follow-up visit 3 (V2): 4 weeks after the 5-day intervention
- **2**Unscheduled follow-up (USV): No limit on number of times

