6.2 Follow-up content: Process schedule

Follow-up time	V0	V1	V 2
Follow-up content	-2w	5d	+4w
Informed consent	×		
Inclusion/exclusion criteria	×		
Demographic data	×		
History taking	×		
check-up	×		
IQ	×		
Autism Diagnostic Observation Schedule (ADOS)/	×		
Autism Diagnostic Interview, Revised (ADI-R)	^		
Childhood Autism Rating Scale (CARS)	×		×
Repetitive Behaviors Scale – Revised (RBS-R)	×	×	×
Social Responsiveness Scale (SRS)	×	×	×
Behavior Rating Inventory of Executive Function(BRIEF)	×	×	×
Conners parent symptom questionnaire (PSQ)	×	×	×
Peabody Picture Vocabulary Test (PPVT)	×		×
Chinese Communication Development Inventory (CCDI)	×		×
Multilingual Assessment Instrument for Narratives (MAIN)	×		×
Clinical Efficacy Rating Scale (CGI)		×	×
Resting-state EEG	×	×	×
Adverse event		×	

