8.0 Safety evaluation

8.1 Physical Signs

Careful physical examination of participants will be conducted by clinician at each visit, with special attention to the inquiry and checking for spasm, convulsions, scalp discomfort, local pain, headache, dizziness, tinnitus, nausea, etc.

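### Section 9.2 ties the serious rTMS reactions to a history of depression and/or syncope, but eligibility does not name syncope and covers depression only as a current disorder: a low-severity precaution

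*Combined protocol and SAP*

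**What the plan says.** Section 9.2 states that rTMS in children carries in principle no safety risk "if the safety guidelines developed by the international expert panel are strictly adhered to". It then acknowledges two serious reactions during stimulation, seizures and neurocardiogenic syncope, and adds: "but subjects who experienced these two adverse reactions had a history of depression and/or syncope".

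Section 4.4 lists nine exclusion criteria, A to I, and the study summary repeats them. Three come near the histories named in 9.2:

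- B: "History of epilepsy or other neurological disease"
- E: "With psychiatric/mental disorder (e.g., very early-onset schizophrenia"), other than ASD
- F: "Suffer from serious heart disease and/or severe hearing impairment"

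Before stimulation, the schedule in 6.2 has a row "History taking" and a check-up row at V0. Section 6.1 lists that visit as "Follow-up visit 1 (V0): Baseline". Section 8.1 adds: "Careful physical examination of participants will be conducted by clinician at each visit".

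**The concern.** The qualification in 9.2 reassures about this trial's children only if children with the histories it names are kept out, or are at least identified and considered. The sentence names two histories. Depression is reached by criterion E when it is current. Syncope is reached by no criterion that mentions it.

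A child who has fainted before, and has neither a neurological diagnosis nor serious heart disease, passes 4.4 as written. That child could then receive 10 sessions a day for 5 days (5.1), which is 10 × 5 = 50 sessions. The point is one of participant safety: an investigator who learns of a faint at V0 finds nothing in the eligibility text that says what to do about it.

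**Working it through.** No statistical figure bears on this point. The check sets the sections side by side.

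**1. Count the criteria.** A to I gives 9 in 4.4 and 9 in the summary. Those naming syncope or fainting: 0 of 9 and 0 of 9. The word syncope occurs twice in the supplied text, both times in the one sentence of 9.2, once as a reaction and once as a prior history.

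**2. Match each history in 9.2 to a criterion.**

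| History in 9.2 | Nearest criterion | Reached? |
|---|---|---|
| Depression, current | E | Yes, as a psychiatric disorder other than ASD |
| Depression, past | E | Not clearly: E is worded in the present, whereas B specifies a history |
| Syncope with a neurological cause | B | Yes, if a neurological disease has been diagnosed |
| Syncope with a serious cardiac cause | F | Yes, if the heart disease is serious |
| Syncope with neither diagnosis | none | No |

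**3. Look for another step that would apply a rule before the first session.**

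- History taking and check-up at V0 (6.2) could bring a faint to light. The table gives no decision rule for any row, which is normal for a schedule, so the rule has to come from 4.4.
- The examination in 8.1 applies at V0 because V0 is listed as a visit. It names 8 symptoms (spasm, convulsions, scalp discomfort, local pain, headache, dizziness, tinnitus, nausea). Syncope is not one of them. Little weight rests on this, since the list is open-ended and concerns signs, not eligibility.
- Section 4.6 A rejects children found not to meet the trial criteria. Prior syncope is not among those criteria.
- Section 9.2 relies on expert-panel guidelines, and a TMS safety guideline is in the reference list. Its content is not in the documents, and 4.4 contains no syncope rule taken from it.

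**4. List what acts after stimulation starts.** There is in-hospital delivery with close follow-up and pediatric treatment (9.2), an interview after each session (8.2), stopping at moderate or severe grade (8.2, 9.2), exit for obvious side effects (4.5 A) and 24-hour reporting of serious adverse events (9.3). None screens for prior syncope, but all limit the consequences of an event.

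**Result.** Current depression is covered. Past depression is not clearly covered, and syncope without a neurological or serious cardiac diagnosis is not covered. Figure 1 is not shown in the supplied text and is not counted as missing.

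**The case against.** The strongest reply is that 9.2 does not establish prior syncope as a risk factor. It joins depression and syncope with and/or and gives no split, count, denominator or citation for the statement. It would be equally true if most affected subjects had depression. This stands, and it rules out any claim about the size of the risk.

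A reader might infer that the protocol contradicts itself. It does not. The sentence is background on reported reactions, placed in a section on recording adverse events, and it never says that such children are screened out. Whether a history mentioned there should become an exclusion is a clinical choice.

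A reader might also infer that a child with prior fainting will be stimulated if the plan is followed to the letter. The documents do not support that. Following the plan includes following the guidelines that 9.2 invokes, and these may or may not address syncope. What can be said is narrower: eligibility under 4.4 as written does not stop that child.

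Finally, a flat exclusion would remove children with one harmless faint for no documented benefit. This also stands, and it argues for a criterion with an exception. It does not argue for leaving the criteria silent on a history that 9.2 uses for reassurance.

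**Conclusion.** The gap is real and of low severity. Syncope is named in 0 of 9 exclusion criteria in both places, and E does not clearly reach past depression. A child with prior fainting and no neurological or serious cardiac diagnosis is eligible under 4.4 as written. How many of the planned minimum of 30 children this concerns is unknown, because the documents give no frequency of prior syncope.

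The conclusion rests on two readings: that E, as worded, means a present disorder, and that simple fainting is neither a neurological disease under B nor serious heart disease under F. It does not rest on any excess risk, since none is shown. It is a precaution that brings eligibility into line with 9.2, and is worth making because the step needed to apply it is already scheduled.

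**What to change.** 1. At the V0 history taking (6.2), ask about prior syncope and past depression, and record both answers in the CRF before the first session.
2. In 4.4 and the summary, add this exclusion: *history of syncope, unless the study pediatrician documents before the first session that it was a single benign faint*. The list goes from 9 to 10 criteria.
3. In both places, word E as *current or past* psychiatric/mental disorder other than ASD.

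**Cost.** One new criterion and one rewording, each in two places; two questions at an existing visit; matching CRF entries; a short note by the pediatrician where the exception is used; and filing the change with the ethics committee (10.1). There is no new visit or procedure, and only one center to instruct (4.2). The downside is that a small, unknown number of otherwise eligible children may be excluded from a single-center trial of about 30. The exception for a single benign faint limits that loss.

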9.3. Serious Adverse Events

Serious adverse events (SAE) are clinical medical events that occur during the course of the study that result in death or life-threatening, require hospitalization or prolonged hospitalization, and cause disability or dysfunctional impairment.

If a serious adverse event occurs during the study, whether related to the intervention, appropriate treatment measures must be taken immediately and reported to the principal investigator and the ethics committee within 24 hours.

10.0 Ethics committee and informed consent form

10.1 Ethics committee

Prior to the start of the study, the protocol and informed consent should be reviewed and approved by the ethics committees of the study centers. During the study, any change of the study protocol to the Ethics Committee shall be filed with the Ethics Committee; in case of serious adverse event, the Ethics Committee shall be notified within 24 hours.

10.2 Informed consent form

Prior to enrollment, the investigator should explain in detail the purpose, procedure, duration, patient benefits and the possible risks of this trial to children's guardians. Informed consent signed in writing by the subject's legal representative should be obtained before enrollment in this study.

11. 0 Data management and statistical analysis

11.1 Data Collection

The data of each subject should be filled in the case report form (CRF) according to the requirements of the study timely, and the investigators should also keep the original data (copy) of participants as much as possible to ensure the accuracy of the CRF data.

11.2 Data Monitoring and Auditing

During the study, the principal investigator and the assisting investigator should monitor the collection and filling of the data regularly, review the data together with the statisticians, and complete the final definition and judgment of the analyzed population.

11.3 Selection of statistical analysis data

Statistical analysis of data from subjects who completed the full 5-day intervention and follow-up assessments (mainly for primary outcome measure, i.e., SRS).

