4.5 Exit criteria

- A. The child had obvious side effects during the intervention
- B. Self-withdrawal (patient withdrawal of consent, etc.)
- C. Lost to visit
- D. Other reasons for the subject's inability to complete the full process of this trial (e.g., severe somatic disease were found after enrollment)

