8.2 Adverse events and incidence

A semi-structured interview was administered following each treatment session and follow-up by the rTMS technician. A standardized adverse events assessment form was completed if adverse events or physical discomfort were reported. Using this form, detailed descriptions of the adverse events experienced were recorded, including rating the event as mild (no impairment, no need stopping trial), moderate (some impairment, need stopping trial, no need for intervention), severe (evidence of impairment, need stopping trial and need for intervention).

9. 0 Adverse events and serious adverse events

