11.4 Statistical analysis of the population

- Analysis of outcome measures: analysis of the population who have completed the corresponding data collection;;
- 2 Safety evaluation: included in the analysis as long as he/her had received one session of intervention.

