11.5 Statistical analysis method

Data will be preprocessed and/or analyzed using SPSS25.0, SAS9.2, Matlab, and R.

• Analysis of the primary outcome measures:

SRS scores at baseline, immediately after the end of 5-day intervention and 4 weeks after the end of 5-day intervention will be analyzed using repeated measures ANOVA.

2 Analysis of other behavioral outcome measures:

RBS-R, BRIEF, PSQ scores at baseline, immediately after the end of 5-day intervention, and 4 weeks after the end of 5-day intervention will be analyzed using repeated measures ANOVA or Friedman test.

CARS, PPVT, CCDI, MAIN scores at baseline and 4 weeks after the end of 5-day intervention will be analyzed using paired-samples t-tests or Mann-Whitney Wilcoxon test.

3 EEG analysis

EEG data will be preprocessed and analysed by MATLAB. Changes in the electrophysiologicalactivity characteristics of the brain at baseline, immediately after the end of 5-day intervention and 4 weeks after the end of 5-day intervention will be analyzed and then correlated with clinical behavioral outcome.

4 Safety evaluation

Summarize the occurrence of adverse events: summarize the number of cases,

Efficacy and mechanistic of repeated transcranial magnetic stimulation in children with autism spectrum disorder: an open-label clinical trial. NCT05472870

Version: 2.0/April 2, 2022

instances, and incidence of adverse events and list all adverse events, those related to the study intervention protocol, serious adverse events, and those leading to exit; list the number of cases, instances, and incidence of mild, moderate, and serious adverse events; give a description for adverse events related to the intervention.

SAnalysis of baseline characteristics

The analysis of baseline characteristics included: demographics (age and gender); baseline analysis of each observation used in this study.

The number of cases, mean, standard deviation, median, minimum and maximum values were calculated when the variables were quantitative indicators; the number of cases and composition ratio were calculated when the variables were categorical indicators.

12. 0 Principal Investigator and contact person

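### The only primary SRS estimate in this uncontrolled trial is a completer estimate, made so jointly by the selection rule in 11.3 and the three-visit ANOVA in 11.5

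*Combined protocol and SAP*

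**What the plan says.** Section 11.3 sets the selection rule, "Statistical analysis of data from subjects who completed the full 5-day intervention and follow-up assessments", and adds in brackets that it applies mainly to the primary outcome, the SRS. Section 11.4 defines the population for outcome measures as "analysis of the population who have completed the corresponding data collection", with no course-completion condition and no exception for the SRS. For safety, a child is "included in the analysis as long as he/her had received one session of intervention".

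Section 11.5 compares "SRS scores at baseline, immediately after the end of 5-day intervention and 4 weeks after the end of 5-day intervention" by repeated measures ANOVA. For safety it lists "serious adverse events, and those leading to exit". It gives no all-treated efficacy analysis, missing-data method or sensitivity analysis.

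Children can leave by several routes. Section 4.5 A is "The child had obvious side effects during the intervention", and 4.5 B is "Self-withdrawal (patient withdrawal of consent, etc"; 4.5 C and D are loss to visit and other reasons. Section 8.2 ties stopping to adverse event grade, for example "moderate (some impairment, need stopping trial, no need for intervention"; the severe grade also requires stopping. Section 4.6 B rejects children who do not cooperate in completing the course. Section 11.2 has the investigators and statisticians settle the analysed population during the study, alongside data review, without saying whether this is done independently of SRS results. Section 4.2 assumes 10% dropout and at least 30 children.

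**The concern.** With no control arm, no comparison group undergoes the same selection. Any difference in SRS change between children who finish and children who do not therefore passes straight into the estimate. At least two exit routes, side effects and adverse events graded as needing a stop, are consequences of the treatment, so the estimate is conditioned partly on tolerating it.

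The Study Summary describes the aim as preliminary exploration. A completer estimate can serve that aim if it is labelled as one. Here it is unlabelled and is the only primary analysis, so a reader would take it as the mean change in children given the course. A larger sample would narrow the confidence interval but leave this bias in place.

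**Working it through.** **1. Which children each rule keeps in the primary analysis.** A standard repeated measures ANOVA uses only children with all three scores.

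| Child | Under 11.3 | Under 11.4 with the 11.5 ANOVA |
|---|---|---|
| Full course, all three SRS scores | in | in |
| Full course, V1 or V2 score missing | out | out |
| Stops early, a later score missing | out | out |
| Stops early, all three SRS scores | out | in |

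The rules differ only in the last row. No section says that the SRS is still collected after early stopping, so that row may hold few children. Deleting 11.3 alone would change little, because the ANOVA removes nearly the same children.

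**2. Inputs.** Section 4.2 gives 30 children, 10% dropout and a standardized effect of 0.5 to 0.8. Then 30 × 0.10 = 3 non-completers and 27 completers. I assume that the 0.5 to 0.8 is in SDs of change. The standard error of a mean change in completers is then 1/√27 = 0.192. The plan gives no figure for this bias, so there is none to reproduce. Everything below rests on assumed responses in non-completers.

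**3. Simple ratio.** Let the non-completers' mean change be f times the completers'. The completer estimate divided by the all-treated mean is 1/(0.9 + 0.1f).

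| f | Ratio | Completer estimate is |
|---|---|---|
| 1.5 | 0.952 | 4.8% too small |
| 1 | 1.000 | unbiased |
| 0.5 | 1.053 | 5.3% too large |
| 0 | 1.111 | 11.1% too large |
| −0.5 | 1.176 | 17.6% too large |

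If only m of the 3 differ from completers, the ratio is 30/(30 − m + mf). For m = 1 it is 1.034 (f = 0) or 1.053 (f = −0.5); for m = 2 it is 1.071 or 1.111.

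In standard errors, the bias is effect × 0.1 × (1 − f)/0.192:
- effect 0.5: 0.26 (f = 0) and 0.39 (f = −0.5);
- effect 0.8: 0.42 and 0.62.

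**4. Stopping that depends on response.** I simulated normally distributed V0, V1 and V2 scores with correlation 0.5, 0.7 or 0.8, SD of change 1 and true change −0.50 at V1 and V2. Ten percent stop before V1. The log-odds of stopping rise with a poorer V1 change, with slope 0.5, 1 or 1.5. Ranges cover the nine settings.

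| Data and method | V1 | V2 |
|---|---|---|
| Completers only | −0.549 to −0.622 | −0.524 to −0.561 |
| Mixed model, baseline only from stoppers | −0.537 to −0.611 | −0.512 to −0.549 |
| Mixed model, later SRS from one third of stoppers | −0.524 to −0.571 | −0.508 to −0.532 |
| Mixed model, later SRS from half of stoppers | −0.517 to −0.552 | −0.506 to −0.523 |
| Completers, dependence reversed | −0.378 to −0.451 | −0.439 to −0.476 |

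The completer bias is 0.25 to 0.63 standard errors at V1 and 0.13 to 0.32 at V2.

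Comparing range ends at V1, the mixed model with baseline only cuts the bias from 0.049 to 0.037 and from 0.122 to 0.111, which is about a quarter and a tenth. With SRS from half the stoppers it falls to 0.017 and 0.052, so 65% and 57% is removed. With one third it falls to 0.024 and 0.071, so 51% and 42% is removed.

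**5. If non-completion is 20%** (24 completers, standard error 1/√24 = 0.204). The steepest slope gives 1.11 standard errors at V1. In the simple ratio, effect 0.8 with f = −0.5 gives 0.8 × 0.2 × 1.5 = 0.24, or 0.24/0.204 = 1.18. The 20% is my assumption.

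**The case against.** **The ANOVA, not 11.3, loses most of these children.** This stands. The loss belongs to 11.3 and 11.5 jointly, and amending only one would achieve little.

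**Sections 11.3 and 11.4 need not conflict.** A reader might infer a flat contradiction. But 11.3 could select the children and 11.4 then apply availability outcome by outcome; the bracketed reference to the SRS in 11.3 fits that reading. The text does not state it, so this is unclear wording rather than an established conflict. The SRS is restricted to completers under the layered reading too.

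**Not every exit reflects intolerance.** Correct. Withdrawn consent, loss to visit and other reasons need not follow from treatment. Non-cooperation under 4.6 B may or may not; no section ties it to tolerability. Section 4.5 itself lists reasons for exit and does not discard data.

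**Every size is assumed.** Also correct. No section links stopping to SRS change, and 4.2 does not say whether its 10% includes rejected or non-compliant cases.

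**The trial is exploratory and about 3 children are involved.** This limits the weight of the point. It does not remove it, because the restriction is explicit and nothing sits beside it for comparison.

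**Conclusion.** The point holds as a should-fix. The textual facts are firm: as planned, the only primary SRS result is a completer estimate, and no all-treated efficacy analysis accompanies it.

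The size is modest under the assumptions shown. At 10% dropout, the bias runs from 4.8% too small to 17.6% too large in the ratio calculation and stays below one standard error in every setting tried, in both directions. That bound depends on the 10%; at 20% non-completion it can exceed one.

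Two stronger readings are not supported. A reader might infer that the effect will be overstated, but it would be understated if non-completers improve more than completers. A reader might also infer from 11.2 that children will be selected on their results; that section is only silent on the matter.

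**What to change.** 1. Reconcile 11.3, 11.4 and 4.6. The primary SRS set is every eligible child with a baseline SRS and at least one session. The only exclusion is ineligibility that already existed at baseline. State in 11.2 that this is judged without reference to SRS outcomes.
2. Ask parents of children who stop early for the V1 and V2 SRS, unless consent is withdrawn. Date both visits from the originally scheduled course, since 6.1 times them only from the 5-day intervention. This step removes most of the bias, provided about half or more of these scores are obtained.
3. Replace the complete-case ANOVA with a mixed model for repeated measures on all available V0, V1 and V2 scores (visit as a factor, unstructured covariance). Note that it helps little where only baseline exists.
4. Report completers as a labelled sensitivity analysis, with completion defined in advance for that analysis. Add one assuming no change in children without a post-baseline SRS and, if wished, one assuming worsening. With 27 completers at −0.50 and 3 missing, no change gives 0.9 × (−0.50) = −0.450, and worsening by 0.25 SD gives −0.450 + 0.1 × 0.25 = −0.425. Give numbers and reasons for all exclusions.

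Cost: wording changes, a standard procedure in software already named in 11.5, up to two extra questionnaires from about 3 families at 10% dropout, and an ethics committee filing under 10.1. The estimate may become smaller. Withdrawals and children lost to visit will mostly stay missing, so some bias may remain; the sensitivity analyses show its range under stated assumptions but do not measure it.
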